5.3.1.3 Sensitivity analyses

The primary analysis may be repeated using additional prognostic covariates (e.g., Parkinsonian age/digital twin). The results will be part of a separate report and may not be part of the CSR.

5.3.1.4 Supplementary approaches

5.3.1.4.1 Supplementary analysis in the absence of ST initiation: de-mediated difference in mean at 12 months

Missing data will be imputed using multiple imputation (MI) according to randomized treatment.

A ‘hypothetical’ handling strategy of ST initiation will be implemented, where all data (up to Month 12) recorded after a participant initiates ST will be corrected using a de-mediation approach.

For further details on the MI and ST de-mediation approaches, see [appendix 5](#).

The population-level summary of interest will be the ST de-mediated difference in target population mean MDS-UPDRS Part I-III sum score at Month 12 as if the participants had not initiated ST between the following treatment arms:

- UCB0599 high dose (360mg/day) and placebo
- UCB0599 low dose (180mg/day) and placebo

ALMEM for longitudinal analysis of covariance (ANCOVA)/repeated measures will be applied to all ST de-mediated data recorded up to Month 12. Treatment, time (visit, categorical) and treatment by time (interaction term between treatment and visit) will be fitted as fixed effects, gender, age at Baseline and Baseline MDS-UPDRS Part I-III will be fitted as covariates. A heterogenous auto-regressive (ARH1) variance-covariance matrix will be fitted to account for the repeated measures within subject.

A summary table presenting the estimated ST de-mediated treatment effects of interest, i.e. difference in means at Month 12 (based on the treatment by time interactions) and corresponding 95% CIs will be produced.

A plot displaying the estimated ST de-mediated means and 95% confidence interval for each treatment group and each time point up to Month 12 will be produced.

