##### Estimator

A LMEM for longitudinal data/repeated measures, similar to the one described for the Primary Efficacy Estimand Estimator (Section 9.3.1.1.1) but with time set as a categorical variable, will be applied to the data up to the initiation of ST.

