- (1) patients for whom MDS-UPDRS at Baseline was not available;
- (2) patients who were already on ST at 3 months;
- (3) patients who had their MDS-UPDRS measured twice or less over the first 12 months of the study.

This left 361 out of the 423 early-stage PD participants in the dataset (participants with SWEDD excluded). This participant sample was assumed to be representative of the POC study placebo arm up to 12 months.

For the purpose of sample size estimation, a closed-form sample size formula for longitudinal data was used (Ahn, 2014 – Chapter 5, formula 5.19).

Number of participants per arm:

$$\frac{\left\{ \left(1 + \frac{1}{\lambda} \right) * \left(1 - \rho \right) + (r_\tau * N_1 * \text{Var}(T)) \right\} * Z_{(1-\frac{\alpha}{2}; \beta)}^2}{N_1 * \text{Var}(T) * \Delta^2}$$

Where λ is the allocation ratio, ρ is the intra-class correlation, r_τ is the ratio of the random slope variance component to the sum of the other variance terms (the random intercept variance component σ_u^2 and the residual variance σ_e^2), ie, $r_\tau = \sigma_{ut}^2 / \sigma^2$ with $\sigma^2 = \sigma_u^2 + \sigma_e^2$. N_1 is the number of timepoints, $\text{Var}(T)$ is the population variance of the timepoints and Δ is the absolute effect size standardized to σ (ie, $\Delta = (0.3 * \beta_t) / \sigma$, where β_t is the time coefficient from the LMEM applied to the PPMI data).

The causes for correlation can be modelled using random effects. The random effects will then induce the correlation structure of the marginal model. The formula used here assumes that the correlation between the participant-specific random intercept and the participant-specific random effect of time (random slope) is null and that $\sigma_{ut}^2 \approx 0$, resulting in a model equivalent to a random intercept model where intra-class correlation (ρ) $\approx \sigma_u^2 / \sigma^2$ for all participants and timepoints.

For the purpose of sample size calculation, the correlation between the random effects was set to 0 when running the LMEM. In practice, this correlation was estimated to be 0.43.

Therefore, in this case the resulting unconditional variance-covariance matrix resembles a compound symmetry working correlation matrix, ie, equivalent to a random intercept model with the variance of observations equaling σ^2 and covariance between observations equaling σ_u^2 .

In addition, the formula assumes the variance components will not differ by treatment group.

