5.3.2.1 Secondary estimands: clinical symptoms (MDS-UPDRS)

These secondary estimands fall under the primary objective of the study, which is to demonstrate the superiority of UCB0599 over placebo with regards to clinical symptoms of disease progression over both 12 and 18 months.

As secondary estimands MDS-UPDRS Part I-III sum score will be analyzed over 18 months and the MDS-UPDRS subscales will be analyzed individually.

In addition, a sub-score based on the MDS-UPDRS Part III and targeted at the early-stage PD population will also be analysed.

For all MDS-UPDRS analyses the treatment comparisons of interest are:

- UCB0599 high dose (360mg/day) and placebo
- UCB0599 low dose (180mg/day) and placebo.

5.3.2.1.1 MDS-UPDRS Part I-III sum score at 18 months, in the absence of ST initiation

Definitions of endpoint

The endpoint for each participant is MDS-UPDRS Part I-III sum score measured bi-monthly over 18 months or up to the time of ST initiation, including Baseline score and scores at 2, 4, 6, 8, 10, 12, 14, 16 and 18 months.

Main analytical approach

Details on the ICE handling for this estimand can be found in [Section 1.2](#). All data recorded after a participant initiates ST will be censored.

A LMEM for longitudinal analysis of covariance (ANCOVA)/repeated measures will be applied to all data recorded up to Month 18. This LMEM will use the same modelling approach described in [Section 5.3.1.4.1](#).

A summary table presenting the treatment effect estimates (based on the treatment by time interactions) with the corresponding 95% confidence intervals will be produced. The estimates at 18 months are the main results to be interpreted.

A plot displaying the adjusted mean and 95% confidence interval for each treatment group from this model will be produced.

Supplementary analyses (regardless of ST initiation)

As a supplementary analysis, the model above will be fitted again using a different ICE handling strategy for ST initiation. Here, the participant-level endpoint will be MDS-UPDRS Part I-III sum score measured bi-monthly over 18 months, regardless of ST initiation. Here ST will be handled using a “treatment policy” strategy where post-ICE data is kept as part of the analysis. The same summary outputs will be produced as described for the main analysis.

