- Retain rows \tilde{Y}_{t+g} where S_{t-1} (lag(g+1)S) = 0 for $t = 1, \dots, T-g$
- Run a linear regression of \tilde{Y}_{t+g} on g -lag outcome Y_t (laggY), observed ST initiation S_t (laggS), and propensity score for ST initiation p_{st} (laggPS), adjusting as above, for $t = 1, \dots, T-g$ in a single step
- Set ψ_g estimates equal to the linear coefficients of S_t (laggS)

- Step 3: obtain de-mediated outcome data points

- Peel off lag effect ψ_1 from outcome Y_{t+1} to obtain the *1-lag de-mediated* outcome:
$$\hat{Y}_{t+1} = Y_{t+1} - \psi_1 \times \text{lag1S} \quad \text{for } t = 1, \dots, T-1$$
- Update \hat{Y}_{t+g} to sequentially remove all lag effects:
$$\tilde{\hat{Y}}_{t+g} = \hat{Y}_{t+g} - \psi_g \times \text{laggS} \quad \text{for } t = 1, \dots, T-g$$

In practice, \hat{Y}_{t+g} will only be updated where $\text{laggS} = 1$

6.5.6

End-of-trial Analysis Models

Repeated measures model

A mixed effect model (MEM) for longitudinal analysis of covariance (ANCOVA)/repeated measures will be applied to each $\mathbf{B} \times \mathbf{M}$ bootstrapped/imputed/ST de-mediated dataset to obtain $\mathbf{B} \times \mathbf{M}$ mean differences (i.e., $\theta_{b,m}$, see [section 6.5.7](#)) at Month 12 and Month 18 - as required per MDS-UPDRS endpoint – using all data recorded up to Month 12/Month18, respectively.

Treatment, time (visit, categorical) and treatment by time (interaction term between treatment and visit) will be fitted as fixed effects, gender, age at Baseline and respective Baseline MDS-UPDRS data will be fitted as covariates. A heterogenous auto-regressive (ARH1) variance-covariance matrix will be fitted to account for the repeated measures within subject (SAS PROC MIXED with REPEATED statement). Kenward and Roger adjustment will be used to obtain degrees of freedom. For further details, refer to [Section 5.3.1.4.1](#).

Slope model

A LMEM (random coefficients model) for longitudinal data will be applied to each of the $B \times M$ bootstrapped/imputed/ST de-mediated dataset to obtain $B \times M$ mean differences (i.e. $\theta_{b,m}$, see [section 6.5.7](#)) in slope over 12 and/or 18 months - as required per MDS-UPDRS endpoint – using all data recorded up to Month 12/Month18, respectively.

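### The categorical-time MDS-UPDRS models use one baseline coefficient for every visit; a baseline-by-visit term is an optional, low-cost gain in precision, mainly at Month 18

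*SAP*

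**What the plan says.** SAP 5.3.1.4.1 defines the repeated-measures model for the Part I-III sum score up to Month 12. On the fixed effects: "Treatment, time (visit, categorical) and treatment by time (interaction term between treatment and visit) will be fitted as fixed effects". On baseline: "gender, age at Baseline and Baseline MDS-UPDRS Part I-III will be fitted as covariates". On covariance: "A heterogenous auto-regressive (ARH1) variance-covariance matrix will be fitted to account for the repeated measures within subject". Baseline therefore enters as a main effect only.

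The model is then carried elsewhere. SAP 5.3.2.1.1 (sum score at Month 18) says "This LMEM will use the same modelling approach described in" 5.3.1.4.1. Sections 5.3.1.4.2, 5.3.2.1.2 (supplementary analysis), 5.3.2.1.3, 5.3.2.1.6 and 5.3.2.1.8 do the same with the relevant score. Section 5.3.2.1.4 restates the model for de-mediated Part III and ePD, and 6.5.6 restates it for the bootstrapped and imputed datasets: "gender, age at Baseline and respective Baseline MDS-UPDRS data will be fitted as covariates".

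The protocol's descriptions differ. For the Month 18 sum score in the absence of ST (9.3.1.2.1), the model is "similar to the one described for the Primary Efficacy Estimand Estimator" with categorical time, and the primary estimator places baseline in the response. For Part III and ePD at Month 18 (9.3.1.2.3.1), it is an ANCOVA at that single visit. Neither ties the baseline relation at Month 18 to that at earlier visits.

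On how baseline relates to later scores, SAP 3.1 says of the planning fit that "the correlation between the random effects was set to 0 when running the LMEM", and then: "In practice, this correlation was estimated to be 0.43".

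**The concern.** If participants with higher baseline scores also progress faster, the regression of a later score on baseline steepens with time. A common coefficient is then a compromise, drawn toward the earlier, less variable and better-populated visits. It falls short at Month 18, so some baseline variation that could have been removed stays in the residual.

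Month 18 is the main timepoint for the key secondary sum-score analysis in 5.3.2.1.1. Under censoring at ST initiation it is also the visit with the least data. The SAP's slope models let intercept and slope covary, with the covariance set to 0 only if convergence fails (5.3, and the unstructured random-effects matrix in 6.5.6). The categorical-time models do not allow for the same feature in their mean structure. What is at stake is precision, not validity.

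**Working it through.** **Inputs.** From SAP Table 3-1, for the Part I-III sum score: random intercept variance 154.0, random slope variance 0.43, residual variance 31.1, placebo slope 0.90 points per month, N1·Var(T) 85.57, Z 2.56. From SAP 3.1: intercept-slope correlation 0 for planning, 0.43 as estimated. From SAP 3.2: 143 per arm, 35% data loss at Month 12, then a further 10% + 10% by Month 18, so 55%.

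**Reproducing the plan's figure.** Total variance is 154 + 31.1 = 185.1.
- 1 − ρ = 31.1/185.1 = 0.1680.
- r_τ·N1·Var(T) = (0.43/185.1) × 85.57 = 0.1988.
- Δ² = 0.27²/185.1 = 0.000394.
- With the allocation factor 2 applied to both terms, n = 2 × (0.1680 + 0.1988) × 2.56² / (85.57 × 0.000394) ≈ 142.7, matching 143 per arm.

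**Implied coefficient on baseline.** b(t) = (154 + t·cov)/185.1, with cov = corr × √(154 × 0.43).
- Correlation 0: b = 154/185.1 = 0.83 at every visit.
- Correlation 0.43: cov = 0.43 × 8.14 = 3.50. b(2) = 161.0/185.1 = 0.87; b(12) = 196.0/185.1 = 1.06; b(18) = 217.0/185.1 = 1.17.

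The Table 3-1 variances come from the fit with correlation forced to 0. Variances approximately refitted for 0.43 (138, 0.35 and 32, assuming complete visits at 0, 3, 6, 9 and 12 months) give 0.85 at Month 2 and 1.13 at Month 18.

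**Cost of a common coefficient.** The large-sample ARH(1) fit with one coefficient was compared with visit-specific coefficients, using the sandwich variance of the treatment difference at 143 per arm. Loss was taken as monotone and completely at random.

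| Setting | Common b | Variance ratio | SE, common vs by visit | Worth per arm |
|---|---|---|---|---|
| Month 18, complete data | 0.987 | 1.033 | 1.682 vs 1.656 | 4.6 |
| Month 18, 35%/55% loss | 0.959 | 1.040 | 2.248 vs 2.205 | 5.7 |
| Month 18, 15%/25% loss | 0.976 | 1.036 | 1.863 vs 1.830 | 5.1 |
| Month 18, refitted variances, complete | 0.960 | 1.028 | – | 143 × 0.028 ≈ 4 |
| Month 18, refitted variances, 35%/55% loss | 0.934 | 1.034 | – | 143 × 0.034 ≈ 5 |
| Month 12, 12-month model, complete | 0.947 | 1.019 | 1.326 vs 1.314 | 2.7 |
| Month 12, 12-month model, 35% loss | 0.935 | 1.023 | 1.559 vs 1.542 | 3.3 |

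In the 18-month model with loss, the Month 12 ratio is 1.011 to 1.015.

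**Hand check, complete data at Month 18.** The variance of the score is 154 + 2 × 18 × 3.50 + 0.43 × 18² + 31.1 = 450.4. Given baseline, it is 450.4 − 1.172² × 185.1 ≈ 196. The common coefficient adds (1.172 − 0.987)² × 185.1 ≈ 6.3, and 6.3/196 ≈ 3.2%. The by-visit SE is √(2 × 196/143) = 1.656, as tabulated.

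**Sensitivity to the correlation.** At 0.2 with the same components, the Month 18 ratio is 1.007 to 1.008. At 0 it is 1.000.

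**Effect on power.** Assume 30% slowing extended linearly, 0.27 × 18 = 4.86 points, at one-sided 10%. Power is Φ(4.86/SE − 1.28). With complete data it moves from about 94.6% to 95.1%; with 35%/55% loss, from about 81% to 82%.

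**The case against.** A baseline main effect is a legitimate specification, and under randomization with complete data it does not bias the treatment difference. The study is exploratory, with no multiplicity adjustment. The result also rests on one number: the SAP gives no standard error for the 0.43, which comes from 12 months of an external observational cohort, so Months 14 to 18 extrapolate a linear random-slope model. All of this stands, and it is why the point is optional.

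Several stronger readings are tempting, and the documents do not support them:

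- A reader might infer that the SAP's own parameters imply a coefficient rising from 0.87 to 1.17. They do so only when 0.43 is joined to variances from the zero-correlation fit. The planning parameters as used imply a flat 0.83.
- A reader might compute a Month 18 variance loss of 8% to 9%, worth up to 12 participants per arm. That needs an unstructured covariance. For MDS-UPDRS the SAP plans ARH(1) with compound symmetry as fallback; section 5.3 mentions unstructured only for DaT-SPECT.
- A reader might carry the same figures to Part I, II, III or ePD. Table 3-1 covers the sum score only. The de-mediated analyses also run on multiply imputed, complete datasets with bootstrap percentile intervals, which this calculation does not represent. Where post-ST data are kept, growth as in untreated scores need not hold.
- A reader of 5.3.1.4.1 alone might attach the Month 18 figure to it. That section stops at Month 12, where the loss is about 1% to 2%.

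**Conclusion.** The point holds as a small efficiency gain. The categorical-time MDS-UPDRS models do fix one baseline coefficient across visits. If the 0.43 correlation applies in this trial, that raises the Month 18 variance of the Part I-III treatment difference by about 3% to 4% (SE by 1.4% to 2.0%), worth roughly 4 to 6 participants per arm, and the Month 12 variance by about 1% to 2%. Below that correlation the loss shrinks quickly.

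This assumes Table 3-1 or similar variance components, linear random slopes continuing to Month 18, and loss completely at random. No bias is claimed. The primary slope analysis is unaffected because baseline is part of its response. For the subscales, ePD and de-mediated data, the direction is plausible but the size is unknown. The change is worth making because it is nearly free, not because the planned analysis is invalid.

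**What to change.** Add a baseline-by-visit interaction to the repeated-measures model in SAP 5.3.1.4.1, 5.3.2.1.4 and 6.5.6. It then reaches the sections that reuse the model: 5.3.1.4.2, 5.3.2.1.1 to 5.3.2.1.3, 5.3.2.1.6 and 5.3.2.1.8. Baseline is mean-centred under SAP 5.3, so the treatment contrasts at each visit read as before.

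The cost is SAP wording and one model term: 9 − 1 = 8 extra parameters for models to Month 18, or 6 − 1 = 5 for models to Month 12, among about 430 participants. No new data are needed and the estimands do not change. If the true correlation is 0, the term gains nothing and costs almost nothing.

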5.3.1.4.2 Supplementary analyses (regardless of ST initiation)

As a supplementary analysis, MDS-UPDRS Part I-III sum score will be analyzed using a different ICE handling strategy with respect to ST. Here a “treatment policy” strategy will be used, where post-ST data will be included in the analysis.

A LMEM for longitudinal analysis of covariance (ANCOVA)/repeated measures will be applied to all data recorded up to Month 12. This LMEM will use the same modelling approach described in [Section 5.3.1.4.1](#).

A summary table presenting the estimated treatment effects (based on the treatment by time interactions) and corresponding 95% CIs will be produced, with the estimates at 8, 10 and 12 months as the main results to be interpreted. A plot displaying the adjusted mean and 95% confidence interval for each treatment group from this model will also be produced.

5.3.1.4.3 Supplementary analysis in the absence of ST initiation: de-mediated difference in slope over 12 months

A LMEM (random coefficient model) for longitudinal data (model described in section 5.3.1.2) will also be applied to the MDS-UPDRS Part I-III sum score ST de-mediated data (ST de-mediation described briefly in [section 5.3.1.4.1](#) with further details in [appendix 5](#)) to estimate the difference in ST de-mediated mean slopes between treatment groups.

A summary table presenting these estimates with the corresponding 95% confidence intervals will be produced. A plot displaying the adjusted mean slope and 95% confidence interval for each treatment group from this model will be produced.

5.3.2 Secondary estimands/endpoint analyses

The secondary estimands will be split into 4 sections based on the study objectives: clinical motor symptoms (MDS-UPDRS-related), clinical non-motor symptoms (MoCA), neurodegeneration (DaT-SPECT and total alpha-syn) and initiation/intake of ST. Some secondary estimands are defined over 12 months and others are defined over 18 months. It will be clearly stated which time points should be used in any analyses throughout this section.

5.3.2.1 Secondary estimands: clinical symptoms (MDS-UPDRS)

These secondary estimands fall under the primary objective of the study, which is to demonstrate the superiority of UCB0599 over placebo with regards to clinical symptoms of disease progression over both 12 and 18 months.

As secondary estimands MDS-UPDRS Part I-III sum score will be analyzed over 18 months and the MDS-UPDRS subscales will be analyzed individually.

In addition, a sub-score based on the MDS-UPDRS Part III and targeted at the early-stage PD population will also be analysed.

For all MDS-UPDRS analyses the treatment comparisons of interest are:

- UCB0599 high dose (360mg/day) and placebo
- UCB0599 low dose (180mg/day) and placebo.

5.3.2.1.1 MDS-UPDRS Part I-III sum score at 18 months, in the absence of ST initiation

Definitions of endpoint

The endpoint for each participant is MDS-UPDRS Part I-III sum score measured bi-monthly over 18 months or up to the time of ST initiation, including Baseline score and scores at 2, 4, 6, 8, 10, 12, 14, 16 and 18 months.

Main analytical approach

Details on the ICE handling for this estimand can be found in [Section 1.2](#). All data recorded after a participant initiates ST will be censored.

A LMEM for longitudinal analysis of covariance (ANCOVA)/repeated measures will be applied to all data recorded up to Month 18. This LMEM will use the same modelling approach described in [Section 5.3.1.4.1](#).

A summary table presenting the treatment effect estimates (based on the treatment by time interactions) with the corresponding 95% confidence intervals will be produced. The estimates at 18 months are the main results to be interpreted.

A plot displaying the adjusted mean and 95% confidence interval for each treatment group from this model will be produced.

Supplementary analyses (regardless of ST initiation)

As a supplementary analysis, the model above will be fitted again using a different ICE handling strategy for ST initiation. Here, the participant-level endpoint will be MDS-UPDRS Part I-III sum score measured bi-monthly over 18 months, regardless of ST initiation. Here ST will be handled using a “treatment policy” strategy where post-ICE data is kept as part of the analysis. The same summary outputs will be produced as described for the main analysis.

5.3.2.1.2 MDS-UPDRS Part III subscale: slope of progression over 12 months

Since the Part III subscale captures the majority of the disability scale measured by the MDS-UPDRS sum score in early PD, the same analyses as planned for the primary estimand will be carried out for this subscale at 12 months.

Definition of endpoint

The primary endpoint for each participant is slope of progression in MDS-UPDRS Part III measured bi-monthly over 12 months or up to the time of ST initiation, including Baseline score and scores at 2, 4, 6, 8, 10 and 12 months.

Main analytical approach

This endpoint will be analyzed in the exact same way as the primary estimand, using the same ICE handling strategy (post-ST initiation data will be censored) and the same model (see [Section 5.3.1.2](#)).

The treatment effect estimates will come from the treatment by time interaction. These estimates are to be interpreted as the unit increase in MDS-UPDRS III per month, after adjusting for gender. A summary table presenting these estimates with the corresponding 95% confidence intervals will be produced.

A plot displaying the adjusted mean and 95% confidence interval for each treatment group from this model will also be produced.

Sensitivity analysis

The primary analysis may be repeated using additional prognostic covariates (e.g., Parkinsonian age/digital twin). The results will be part of a separate report and may not be part of the CSR.

Supplementary analyses (regardless of ST initiation)

As a supplementary analysis, MDS-UPDRS Part III will be analyzed using a different ICE handling strategy with respect to ST initiation. Here a “treatment policy” strategy will be used, where post-ST initiation data will be included in the analysis.

A LMEM for longitudinal analysis of covariance (ANCOVA)/repeated measures will be applied to all data recorded up to Month 12. This LMEM will use the same modelling approach described in [Section 5.3.1.4.1](#) (baseline Part III score will be used in place of Part I-III sum score).

A summary table presenting the estimated treatment effect (based on the treatment by time interactions) and corresponding 95% CIs will be produced, with the estimates at 8, 10 and 12 months as the main results to be interpreted. A plot displaying the adjusted mean and 95% confidence interval for each treatment group from this model will also be produced.

5.3.2.1.3 MDS-UPDRS Part III subscale: difference in mean at 12 and at 18 months

Definition of endpoint

The endpoint for each participant is MDS-UPDRS Part III score measured bi-monthly over 18 months or up to the start of ST, including Baseline score and scores at 2, 4, 6, 8, 10, 12, 14, 16 and 18 months.

Main analytical approach

Details on the ICE handling for this estimands can be found in [Section 1.2](#). All data recorded after a participant initiates ST will be censored.

A LMEM for longitudinal analysis of covariance (ANCOVA)/repeated measures will be applied to all data recorded up to Month 18. This LMEM will use the same modelling approach described in [Section 5.3.1.4.1](#) (baseline Part III score will be used in place of Part I-III sum score).

A summary table presenting the treatment effect estimates (based on the treatment by time interaction) with the corresponding 95% confidence intervals will be produced. The estimates at Month 12 and Month 18 are the main results to be interpreted.

A plot displaying the adjusted mean and 95% confidence interval for each treatment group from this model will be produced.

Supplementary analyses (regardless of ST initiation)

As a supplementary analysis, MDS-UPDRS Part III will be analyzed using a different ICE handling strategy with respect to ST initiation. Here, a “treatment policy” strategy will be used, where post-ST initiation data will be included in the analysis. The same modelling approach as described above for the main analysis will be used.

5.3.2.1.4 MDS-UPDRS Part III subscale and ePD subscore: de-mediated difference in mean at 12 and at 18 months

Definition of endpoints

MDS-UPDRS Part III subscale and Part III ePD subscore measured bimonthly over 18 months, including Baseline score, and scores at 2, 4, 6, 8, 10, 12, 14, 16, and 18 months.

The analysis below will be conducted using all data recorded up to Month 18, for the two endpoints (subscale / ePD subscore).

Main analytical Approach

Missing data will be imputed using multiple imputation (MI) according to randomized treatment.

A ‘hypothetical’ handling strategy of ST initiation will be implemented, where all data (up to Month 18) recorded after a participant initiates ST will be corrected using a de-mediation approach.

For further details on the MI and ST de-mediation approaches, see [appendix 5](#).

The population-level summary of interest will be the ST de-mediated difference in target population mean MDS-UPDRS Part III subscale/ePD subscore at Month 12 and Month 18 as if the participants had not initiated ST between the following treatment arms:

- UCB0599 high dose (360mg/day) and placebo
- UCB0599 low dose (180mg/day) and placebo

A LMEM for longitudinal analysis of covariance (ANCOVA)/repeated measures will be applied to all ST de-mediated data recorded up to Month 18. Treatment, time (visit, categorical) and treatment by time (interaction term between treatment and visit) will be fitted as fixed effects, gender, age at Baseline and Baseline MDS-UPDRS Part III subscale (ePD subscore) will be fitted as covariates. A heterogenous auto-regressive (ARH1) variance-covariance matrix will be fitted to account for the repeated measures within subject.

A summary table presenting the ST de-mediated estimates for the treatment effects of interest, i.e. difference in means at Month 12 / Month 18 (based on the treatment by time interactions) and corresponding 95% confidence intervals will be presented.

A plot displaying the ST de-mediated estimated means and 95% confidence interval for each treatment group and each time point up to Month 18 will be produced.

Supplementary analyses (in the absence of ST initiation – ST de-mediated)

A LMEM (random coefficient model) for longitudinal data (model described in section 5.3.1.2) will also be applied to the MDS-UPDRS Part III subscale (ePD subscore) ST de-mediated data (ST de-mediation described briefly in section 5.3.1.4.1 with further details in section 6.5) to estimate the difference in ST de-mediated mean slopes between treatment groups.

A summary table presenting these estimates with the corresponding 95% confidence intervals will be produced. A plot displaying the adjusted mean slope and 95% confidence interval for each treatment group from this model will be produced.

